10.2 Biochemical (PSA) response

PSA response will be determined by comparing the PSA levels after therapy to the baseline, pre-treatment PSA. Declines of $\geq 30\%$ confirmed by a second PSA value ≥ 2 weeks later, will be reported. Subjects must not demonstrate clinical or radiographic (CT and/or MR) evidence of disease progression during this time period.

10.3 Duration of PSA response

Duration of PSA response is defined as the time from the first 25% PSA decline until the PSA value is confirmed to increase by 25% above the nadir, provided that the increase is at least 2 ng/mL above the nadir.

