10.5 PSA Progression

PSA progression will be defined as a rise of > 25% above either the pretreatment level or the nadir PSA level (whichever is lowest). PSA must increase by > 2 ng/ml to be considered progression. Confirmation requires a second consecutive rising PSA at least 2 weeks apart.

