10.6 PSA Stabilization

PSA stabilization is referred to as any set of PSA values that do not meet the criteria for PSA response or PSA progression.

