10.7 Time to PSA Progression

Time to PSA progression is defined as the interval between initiating treatment until the PSA rises 25% above nadir provided that the increase is at least 2 ng/mL.

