12.2. Phase II Study Design/Endpoints

We will enroll up to 27 subjects into the Phase II portion (including the 3-6 used for establishing the MTD). We will define evaluable patients as patients who met eligibility requirements, have initiated therapy, and were not removed from the study for non-compliance or patient withdrawal.

Sample size recommendations for the two-stage design are determined according to Simon's two-stage minimax design. We project a 30% PSA decline proportion of 35%, below which the regimen will be unacceptable and a 30% PSA decline proportion of 60%, above which the regimen will be considered worthy of further exploration. The null hypothesis that the 30% PSA decline proportion is less than or equal to 35% will be tested against the alternative hypothesis that the 30% PSA decline proportion is greater than or equal to 60%.

The sample size computations were performed assuming a 0.10 one-sided level of significance and 90% power assuming a historical control value for PSA decline of 35% and the alternative

hypothesis of 60%. If 6 or fewer of the first 16 evaluable patients do not experience a 30% decline in PSA (stage 1), the study will be terminated and declared to have a negative result. If 7 or more patients out of the first 16 evaluable patients experience a 30% decline in PSA, ongoing accrual will proceed to the target sample size of 27 patients (stage 2). The new regimen will be declared active in this patient population and worthy of further testing if 13 or more patients experience a 30% PSA decline among the 27 patients entered. This two-stage design yields a 0.90 probability of a positive result if the true 30% PSA decline proportion is 60%. It yields a 0.90 probability of a negative result if the true 30% PSA decline proportion is 35%. An exact 95% binomial confidence interval will be constructed for the proportion of patients with PSA decline.

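### PSA response duration starts at a 25% decline although response needs a confirmed 30%, and time to PSA progression restates its event without the confirmation and reference level set in 10.5

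*Combined protocol and SAP*

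**What the plan says.** The rules stand in adjacent subsections of section 10 of the combined protocol and SAP.

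- **10.2, response:** a decline of at least 30% from baseline, "confirmed by a second PSA value" at least 2 weeks later, with no clinical or radiographic progression meanwhile. The phase II rule in 12.2 uses the same size of decline: the regimen is declared active "if 13 or more patients experience a 30% PSA decline among the 27 patients entered".
- **10.3, duration of response:** "the time from the first 25% PSA decline" "until the PSA value is confirmed to increase by 25% above the nadir", with an increase of at least 2 ng/mL.
- **10.5, progression:** a rise of more than 25%, and of more than 2 ng/mL, above the lower of the pretreatment value and the nadir. "Confirmation requires a second consecutive rising PSA at least 2 weeks apart".
- **10.6, stabilization:** PSA values that "do not meet the criteria for PSA response or PSA progression".
- **10.7, time to progression:** from the start of treatment "until the PSA rises 25% above nadir provided that the increase is at least 2 ng/mL".

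Biochemical PFS by PCWG3 criteria is a secondary objective (1.2). The efficacy analysis at the end of 10.8 plans a Kaplan-Meier median for it. Section 10 gives it no definition of its own.

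**The concern.** A duration of response should begin when the response begins, and a time to progression should end at the event that the plan calls progression. Neither link holds here. A 25% decline defines response nowhere in the documents, so 10.3 starts the clock at a point that 10.2 does not recognise. Section 10.7 does not point to 10.5. It describes the event again and leaves out two of its parts, the confirmation and the choice between pretreatment value and nadir.

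Two analysts, one following 10.5 and one following 10.7, could report different event counts and dates from the same PSA series. With at most 27 patients in phase II, a few reclassified events could move a median. If the rule is not settled beforehand, the choice would be made with the data in view.

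**Working it through.** The plan attaches no figure to either measure, so the check compares the rules and then illustrates size under stated assumptions.

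**1. Start of duration (10.2 against 10.3).** Take a constructed responder with baseline 100 and later draws of 74, 68 and 66.
- Declines are 26%, 32% and 34%.
- Under 10.2 the threshold is first met at 68 and confirmed at 66 (draws at least 2 weeks apart). Under 10.3 the clock starts at 74, one draw sooner.
- For the same end date, an earlier start can only leave the duration equal or make it longer. A patient who crosses 25% and 30% at the same draw is unchanged.

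Size, assuming an exponential fall with halving time T weeks: the gap between the 25% and 30% points is 7 × T × ln(0.75/0.70) / ln 2 days.
- T = 4: 2.8 days
- T = 8: 5.6 days
- T = 12: 8.4 days

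Nominal PSA draws are 2 to 4 weeks apart (Table 15 and section 6.1). Each gap is shorter than 14 days, so the start moves by at most one draw. The halving times are assumptions.

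**2. Confirmation (10.5 against 10.7).** Baseline 100, then 80, 60, 76, 61, 60.
- The nadir before the rise is 60, and 1.25 × 60 = 75.
- The value 76 exceeds 75 and lies 16 ng/mL above nadir, so 10.7 as written records an event.
- The next value, 61, is not a second rise, so 10.5 records none.

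**3. Reference level (10.5 against 10.7).** Baseline 50, then 60, 65, 70.
- Under 10.5 the reference is 50 and the threshold 1.25 × 50 = 62.5. It is met at 65 and confirmed at 70.
- Under 10.7, if nadir means the lowest value after treatment (60), the threshold is 1.25 × 60 = 75, which is not reached.
- If nadir includes baseline, the two references agree and this difference disappears.

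Step 2 gives 10.7 an extra event and step 3 takes one away. Only if nadir includes baseline are the confirmed 10.5 events a subset of the 10.7 events.

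**4. Illustration of step 2.** Assumptions, none from the documents: true PSA flat at 50 ng/mL in every patient, independent lognormal variation between draws, nadir including baseline, draws to 24 weeks, 100,000 simulated patients. The columns give the share with at least one event.

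| Within-patient CV | Table 15 days, unconfirmed | Table 15 days, second consecutive rise | Days with 6.1.2.3 draws added, unconfirmed | Days with 6.1.2.3 draws added, second rise |
|---|---|---|---|---|
| 5% | 1.9% | 0.0% | 2.9% | 0.1% |
| 10% | 58.7% | 10.6% | 71.6% | 16.2% |
| 15% | 87.9% | 31.9% | 94.6% | 44.1% |
| 20% | 95.5% | 47.2% | 98.6% | 61.6% |

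This shows that confirmation can matter a good deal when PSA is noisy. It does not estimate the effect in this trial.

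**5. Phase II design.** The rule of at least 7 of 16, then at least 13 of 27, for 35% against 60% has exact one-sided alpha 0.0979 and power 0.9001, against the stated 0.10 and 0.90. It depends on the 30% endpoint and on neither 10.3 nor 10.7.

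**The case against.** The best defence concerns 10.7. Its heading uses the term that 10.5 defines, and it is silent on confirmation; it does not say that an unconfirmed rise suffices. A careful analyst might carry the rule over from 10.5. That is a fair reading, but the text does not secure it: 10.7 spells out an event with size and minimum increase, gives no cross-reference, and omits the confirmation that 10.3 does state for its own end point.

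Three stronger readings are tempting, and the documents do not support them.

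- *A reader might infer that biochemical PFS is shortened.* No section makes 10.7 the biochemical PFS event. Section 1.2 cites PCWG3, and the efficacy analysis names only the Kaplan-Meier method. The direction is not uniform either, as the 50, 60, 65, 70 series shows.
- *A reader might infer that duration is computed in the wrong patients.* A man whose best decline is 25 to 29% has stabilization under 10.6 if he has not progressed, and he would have a 10.3 start date. But the heading of 10.3 presupposes a response, and nothing there says non-responders are included. The firm error is the start threshold.
- *A reader might infer that every rise is dated too early under 10.7.* If progression is dated at the first qualifying value, a rise confirmed at the next draw keeps its date, apart from the reference question. Only rises that are not confirmed change the result.

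The low stakes also stand. Neither measure is a listed objective, and 12.5.2 analyses PSA response descriptively.

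**Conclusion.** Wrong as written, and minor.

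The mismatch in 10.3 is plain. For a responder the start can precede the response threshold, by at most about one draw under a steady decline with the assumed halving times. With the end date unchanged, duration is the same or longer.

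Section 10.7 gives an event that differs from 10.5 in confirmation and, depending on what nadir means, in reference level. Time to PSA progression can count isolated rises that are never confirmed. If nadir excludes baseline, it can miss or delay progression in patients whose PSA never falls. The net direction is therefore not certain. The same applies to biochemical PFS only if it is built on 10.7.

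The number of patients affected cannot be derived, because the documents give no PSA variability or trajectories. The primary endpoint, the Simon boundaries, alpha and power do not change.

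**What to change.** - **10.3:** measure duration from the first PSA value that meets the 10.2 response (a decline of at least 30%, later confirmed), in responders only.
- **10.7:** replace the restated event with the time from first treatment to the first PSA value that meets PSA progression as defined in 10.5, including its confirmation and its pretreatment-or-nadir reference. This also settles that the first qualifying value, not the confirming one, sets the date.
- **Inequalities:** use one form throughout. Section 10.5 asks for more than 25% and more than 2 ng/mL, while 10.3 and 10.7 ask for 25% and at least 2 ng/mL.
- **Biochemical PFS:** state that its PSA component uses this same event.

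The cost is two rewritten definitions and one added sentence. No new data, visits or patients are needed, and the sample size stays as it is. The change should be made before the PSA data are analysed.

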10.4 Duration of CTC response

Duration of CTC response is defined from the first CTC count drop to <5 (or $\leq 50\%$ of baseline) to the time CTC count increases to ≥ 5 (or $\geq 25\%$ increase from nadir).

10.5 PSA Progression

PSA progression will be defined as a rise of > 25% above either the pretreatment level or the nadir PSA level (whichever is lowest). PSA must increase by > 2 ng/ml to be considered progression. Confirmation requires a second consecutive rising PSA at least 2 weeks apart.

10.6 PSA Stabilization

PSA stabilization is referred to as any set of PSA values that do not meet the criteria for PSA response or PSA progression.

10.7 Time to PSA Progression

Time to PSA progression is defined as the interval between initiating treatment until the PSA rises 25% above nadir provided that the increase is at least 2 ng/mL.

10.8 Change in lesion size

In subjects with measurable disease, complete response (CR) is defined as complete disappearance of all measurable and evaluable lesions by physical examination or imaging studies and normalization of PSA with no appearance of new lesions for > 1 month. Partial response (PR) is defined as a 30% or greater reduction in the sum longest uni-dimensional diameter of all measurable lesions. There may be no new lesions. Stable Disease (SD) is characterized by subjects who do not meet the criteria of PR and who are without signs of progressive disease for at least 1 month. Disease Progression (DP) is defined as a greater than 20% increase in the sum longest uni-dimensional diameters of the indicator lesions or the appearance of new lesions. Bone scan progression (evaluable disease only) is requires at least 2 new lesions seen on a scan subsequent to baseline followed by a repeat scan at least 6 weeks later with at least one new additional lesion.

Conventional Imaging studies (MRI, CT, Bone Scan) along with optional but recommended investigational images (⁶⁸Ga-PSMA-HBED-CC PET/CT imaging and Lutetium-177 Planar/SPECT imaging) will be performed during the study visits or as clinically indicated to assess disease response. In subjects enrolled in this study, the measurable disease response will be calculated using Response Evaluation Criteria in Solid Tumors (RECIST Version 1.1) with PCWG3 modifications.

Radiographic scans will be used to assess best overall response and radiographic progression based on modified RECIST criteria for soft-tissue lesions and protocol-specific criteria for bone lesions. Baseline images should be taken during Screening as close as possible to, and never more than 28 days before treatment visit #1. Every effort must be made to ensure the same radiographic method is used before and after treatment at scheduled visits. Radiographic progression free survival will be evaluated based on these results.

Analysis of Efficacy:

Median bPFS, rPFS, and OS, including survival curves, will be estimated using Kaplan-Meier methodology. Greenwood's formula will be used to calculate 95% confidence intervals for the Kaplan-Meier estimates. Percent change in PSA from baseline will be described by mean/median and standard deviation/inter-quartile range, as appropriate, depending on the distribution of percent change from baseline. Modified RECIST response (i.e., CR, PR, and CR/PR proportions), CTC count response proportion, defined favorable LDH/CTC proportion, and associated 95% confidence intervals, will be estimated via binomial proportions.

All subjects will be offered optional but recommended baseline and subsequent ⁶⁸Ga-PSMA-HBED-CC PET/CT, and those treated with ¹⁷⁷Lu-labeled products will undergo Planar/SPECT imaging. We will analyze the data for associations with response to treatment as well as survival by chi-square tests/Fisher's exact tests and log-rank tests, respectively. For pre/post imaging comparisons, McNemar's chi-square test and paired t-tests/Wilcoxon signed-rank tests will be used, as appropriate. We plan to report data for each individual study as well as across the studies.

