1.2 Secondary Objectives

- To assess radiographic response rate by RECIST 1.1 with PCWG3 modifications
- To assess biochemical and radiographic progression-free survival by PCWG3 criteria
- To assess overall survival following treatment with the combination of ^{177}Lu -J591 and ^{177}Lu -PSMA-617 in a 2-week dose-fractionation regimen
- To assess safety of treatment with the combination of ^{177}Lu -J591 and ^{177}Lu -PSMA-617 in a 2-week dose-fractionation regimen as assessed by CTCAE 4.0
- To assess changes in CTC count as measured by CellSearch and the rate of favorable CTC count and LDH at 12 weeks following treatment with the combination of ^{177}Lu -J591 and ^{177}Lu -PSMA-617 in a 2-week dose-fractionation regimen
- To assess patient reported outcomes using FACT-P and the Brief Pain Inventory short form

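### Section 10.8 lets the same new bone lesion be scored two ways for rPFS, and leaves the event date, reference sum and CR definition unsettled

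*Combined protocol and SAP*

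**What the plan says.** Four pieces of text bear on radiographic progression and response.

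- **Measurable-disease list (10.8, first paragraph).** It opens: "In subjects with measurable disease, complete response (CR) is defined as complete disappearance of all measurable and evaluable lesions". CR also needs a normal PSA. Progression is more than 20% growth in the summed diameters of the "indicator lesions or the appearance of new lesions".
- **Bone rule (same paragraph).** It begins: "Bone scan progression (evaluable disease only) is requires at least 2 new lesions seen on a scan subsequent to baseline". Confirmation then takes another scan, no sooner than 6 weeks afterwards, that shows one or more further lesions.
- **Site-based split (10.8, third paragraph).** Scans are used to assess "radiographic progression based on modified RECIST criteria for soft-tissue lesions and protocol-specific criteria for bone lesions", and rPFS is evaluated on those results. The second paragraph names RECIST 1.1 with PCWG3 modifications for measurable disease response.
- **Objective (1.2, repeated in the Protocol Summary).** "To assess biochemical and radiographic progression-free survival by PCWG3 criteria". Radiographic response is a separate secondary objective, by RECIST 1.1 with PCWG3 modifications.

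Under Analysis of Efficacy in 10.8, rPFS is estimated by Kaplan-Meier, and CR, PR and CR/PR are reported as binomial proportions with 95% intervals. Imaging is mandatory at the Day 85 ± 7 efficacy visit. Table 15, footnote h, then recommends it about every 12 weeks until radiographic progression, as standard care.

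**The concern.** A time-to-event endpoint needs one event rule that two readers would apply alike. Here the new-lesion criterion in the measurable-disease list is unqualified, while the more demanding bone rule carries a tag whose meaning is left open. Whether a new bone-scan lesion ends a man's rPFS can then depend on how the reader takes the tag and on whether the man also has measurable disease. The Kaplan-Meier curve could mix two event definitions.

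This may not be repairable afterwards. Repeat imaging is recommended only until radiographic progression, and the four-weekly visits in 6.1.4 cease to be required once it occurs. If progression is called on an unconfirmed bone lesion, the scan that would have confirmed or refuted it may never be done.

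For response, a PSA condition inside CR means that the reported CR proportion is not purely radiographic.

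**Working it through.** The plan states no power, event target or test for rPFS, so there is no figure to reproduce. The check is a comparison of texts, with simple arithmetic for scale.

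**1. What the tag can mean.**
- *Patient level:* men who have only evaluable disease. Men with measurable disease then have no bone rule of their own, and only the unqualified new-lesion criterion is left.
- *Lesion level:* bone-scan lesions belong to the evaluable class. The bone rule then covers everyone, but nothing removes bone lesions from the new-lesion criterion. The list is not confined to soft tissue, since its CR definition covers evaluable lesions too.

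**2. Whether the site-based paragraph settles it.** It sends bone to protocol-specific criteria. The only bone criteria in the documents are the tagged sentence, so the reader returns to step 1.

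**3. Consequence for a man with a measurable node and new bone lesions at Day 85.**

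| Bone scans | Scored by the list | Scored by the bone rule |
|---|---|---|
| One new lesion, none later | Progression could be called at Day 85 (no count is given) | No event |
| Two new lesions, none later | Progression at Day 85 | No event |
| Two new lesions, another on the repeat scan | Progression at Day 85 | Event, date not stated |

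**4. Event date.** Earliest confirmation: 85 + 6 × 7 = Day 127. On the 12-week schedule: 85 + 12 × 7 = Day 169. Dating at confirmation moves the event by 127 − 85 = 42 days to 169 − 85 = 84 days. Dating at the scan that showed the new lesions moves it by 0.

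**5. Reference sum.** Take a man whose sum has fallen by exactly 30%, the PR threshold, to 0.70 of baseline. Measured from the smallest sum, 20% growth is reached at 0.70 × 1.20 = 0.84 of baseline. Measured from baseline, it is reached at 1.20. Section 10.8 does not say which applies, whereas the PSA rule in 10.5 does name its reference (the lower of pretreatment and nadir).

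**6. CR.** A man whose lesions have all disappeared but whose PSA is not normal fails CR. He still meets the 30% reduction for PR, so the CR/PR split moves while the combined proportion need not.

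**7. How many men could be affected (illustration only).** In the earlier fractionated ¹⁷⁷Lu-J591 trial (section 2.3.1.2), 83.7% had bone and 61.2% nodal metastases. The share with both is at least 83.7 + 61.2 − 100 = 44.9% and at most 61.2%. Applied to 27 men: 0.449 × 27 = 12.1 and 0.612 × 27 = 16.5, so about 12 to 17. These men could have a bone finding to which both rules might apply; this is not a rate of discordant events.

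**The case against.** The strongest reply is that the third paragraph of 10.8, on which rPFS is expressly based, assigns criteria by lesion site with no exception for men with measurable disease. On that reading every bone-scan lesion goes to the two-lesion rule with confirmation, and the tag merely records that bone lesions are evaluable rather than measurable. This is a plausible reading and may well be the intended one. It stands to this extent: a definite double rule is not shown. It does not remove the ambiguity, because the paragraph relies on the tagged sentence for its bone criteria and nothing excludes bone from the new-lesion criterion.

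Three stronger readings are tempting and should not be drawn:
- **That a single new lesion is definitely immediate progression in men with measurable disease.** The text uses an unqualified plural and does not mention bone, so this is an inference.
- **That neither rule in 10.8 matches PCWG3.** The documents do not reproduce the PCWG3 rules. Only the difference in named criteria can be seen.
- **That the phase II decision is affected.** Section 10.2 does require absence of radiographic progression for a PSA response, but it names CT and/or MR, not bone scan. The documents do not show that the bone-scan ambiguity reaches the PSA count.

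The reference-sum point is partly met, since RECIST 1.1 is named as the governing standard in 9.2, 10.8 and 12.5.2. The paraphrase in 10.8 is still incomplete beside it.

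**Conclusion.** Section 10.8 does not give one workable definition of radiographic progression. The same new bone lesion can be scored two ways, the date of a confirmed bone event is open by 42 to 84 days if it is counted at confirmation (nominal Day 85 scan, next scan at 6 to 12 weeks), and the growth criterion lacks its reference sum. CR carries a PSA condition that the radiographic objective does not mention. The criteria named in 10.8 and in the objective are not reconciled.

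The weight is moderate. rPFS and the CR and PR proportions are descriptive secondary endpoints with no test attached, and the phase II decision rests on the 30% PSA decline. The 44.9% to 61.2% overlap assumes the earlier trial's case mix and lets nodal disease stand in for measurable disease, so it shows only that the situation would not be rare. The text should be amended, ideally before further scans are read, because a premature call of progression may end the imaging needed to correct it.

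**What to change.** Amend the wording of 10.8 so that the site-based split applies to every patient:

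- Limit the new-lesion criterion in the measurable-disease list to soft-tissue lesions.
- Delete the parenthesis *evaluable disease only* from the bone rule, so that it holds whether or not measurable disease is present.
- State that bone progression, once confirmed, is dated at the scan on which the new lesions were first seen.
- State the reference sum for the growth criterion under the named RECIST 1.1.
- Remove PSA normalisation from radiographic CR.
- Reconcile the protocol-specific bone criteria with the PCWG3 criteria named in the objective, so that one set governs.

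The cost is protocol wording only. The CT/MRI and bone scans already in the schedule suffice, and sample size is unaffected. If scans have already been read under 10.8, those calls should be checked against the amended rule.
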